#### 7 STUDY INTERVENTION(S) AND CONCOMITANT THERAPY

Study intervention is defined as any investigational intervention(s), marketed product(s), placebo, procedure(s) or medical device intended to be administered to a study participant according to the study protocol.

Study intervention includes both investigational [medicinal] product (IP/IMP) and non-investigational [medicinal] product (non-IP/non-IMP) as indicated in Table 7.1-1.

An IP, also known as IMP in some regions, is defined as a pharmaceutical form of an active substance or placebo being tested or used as a reference in a clinical study, including products already with a marketing authorization but used or assembled (formulated or packaged) differently from the authorized form, or used for an unauthorized indication, or when used to gain further information about the authorized form.

Other medications used as support or escape medication for preventative, diagnostic, or therapeutic reasons, as components of the standard of care for a given diagnosis, may be considered as non-IPs.

# 7.1 Study Interventions Administered

The selection and timing of dose for each participant is presented in in Table 7.1-1.

**Table 7.1-1:** Study Interventions

Arm Name	Deucravacitinib (BMS-986165)	Placebo
Intervention Name	Deucravacitinib (BMS-986165)	Placebo for deucravacitinib
Туре	Drug	Drug
Dose Formulation	Tablet	Placebo tablet to match deucravacitinib
Unit Dose Strength(s)	6 mg	n/a
Dosage Level(s)	1 active tablet QD in the morning	1 placebo QD in the morning
Route of Administration	Oral	Oral
Use	Experimental	Placebo
IMP and NIMP/AxMP	IMP	IMP
Sourcing	Provided centrally by the Sponsor	Provided centrally by the Sponsor
Packaging and Labeling	Study intervention will be provided in a bottle. Each bottle will be labeled as required per country requirement.	Study intervention will be provided in a bottle. Each bottle will be labeled as per country requirement.

AxMP, auxiliary medicinal products; IMP, investigational medicinal product; n/a, not applicable; NIMP, non-investigational medicinal product; QD, once daily.

## 7.2 Method of Study Intervention Assignment

Before the study is initiated, each user (at investigative sites) will receive log-in information and directions on how to access the IRT system. At the time of the Screening Visit, immediately after informed consent is obtained and before any study-related procedures are performed, the investigative site will access the enrollment option of the IRT system for assignment of a participant number for all participants, including participants not subsequently randomized or treated. The participant number is assigned sequentially by the system and will be unique across all sites. All enrolled participants will be assigned sequential participant numbers. The participant number will not be used for any other participant. If a participant is rescreened, they will be given a new identification number.

At Day 1, participants who meet all criteria for enrollment at Screening and Day 1 will be centrally randomized in a 2:1 ratio to deucravacitinib 6 mg QD or placebo as determined by a computer-generated randomization schedule using IRT. The randomization lists will be generated by the IRT vendor using a permuted block design within each stratum level.

After all inclusion/exclusion criteria have been met for a participant, the investigative site will access the IRT on Day 1 for the purpose of randomizing a participant. An intervention group will be assigned by IRT based on the above-described randomization schedule. In addition, a unique kit number will be assigned to the participant corresponding to the intervention assignment.

Study intervention will be dispensed at study visits as shown in the Schedule of Activities (Section 2). When new intervention kits need to be provided, the investigative site will access the IRT to obtain the kit number to assign to the participant.

At Week 16, all participants, regardless of their blinded intervention, will be switched to open-label deucravacitinib 6 mg QD bottles through Week 52.

#### 7.3 Blinding

This is a randomized, double-blind, placebo-controlled study.

#### 7.3.1 Maintaining the Blind

Blinded intervention assignments will be managed using IRT. IP supply will be controlled by IRT at each visit.

All tablets are identical in appearance and will be supplied in bottles with each daily dose made up of the appropriate combination of active and/or placebo tablets to provide the correct intervention, as shown in Table 7.1-1. Investigative site staff, Sponsor and designee personnel, and participants and their families will remain blinded to intervention assignments.

The Sponsor and site facing study team will be unblinded to the individual treatment assignments at the primary endpoint database lock after the last participant has completed the Week 16 visit.

Clinical Protocol BMS-986165

The primary analysis database lock will occur after all randomized participants completed their Week 16 visit or discontinued prior to Week 16. The study participants and investigators will remain blinded to the initial treatment assignment throughout the study.

## 7.3.2 Circumstances for Unblinding

Blinding of study treatment assignment is critical to the integrity of this clinical study. However, in the event of a medical emergency or pregnancy in an individual participant in which knowledge of the IP is critical to the participant's management, the blind for that participant may be broken by the investigator. The participant's safety takes priority over any other considerations in determining if a treatment assignment should be unblinded.

Before breaking the blind of an individual participant's treatment, the investigator should determine that the unblinded information is necessary (ie, that it will alter the participant's immediate management). In many cases, particularly when the emergency is clearly not related to the IP, the problem may be properly managed by assuming that the participant is receiving the IP.

It is highly desirable that the decision to unblind treatment assignment be discussed with the Medical Monitor, but the investigator always has ultimate authority for the decision to unblind. The actual task of unblinding can be delegated by the investigator to a designee assigned the task on the Delegation of Authority. The Principal Investigator or appointed designee should only call in for emergency unblinding after the decision to unblind the participant has been documented.

For this study, the method of unblinding for emergency purposes is described in the IRT manual.

In case of an emergency, the investigator has unrestricted access to randomization information via IRT and is capable of breaking the blind through the IRT system without prior approval from the Sponsor. After the unblinding, the investigator shall notify the Medical Monitor or designee and/or study director. Participant and unblinded treatment information and the reason for the blind being broken must be recorded on the appropriate study status page of the eCRF. After unblinding via IRT, the investigator shall notify the Medical Monitor or designee.

In cases of accidental unblinding, contact the Medical Monitor and ensure every attempt is made to minimize additional disclosure and the impact of unblinding.

Any request to unblind a participant for nonemergency purposes should be discussed with the Medical Monitor.

If a participant is unblinded for any reason, the participant will be discontinued from treatment.

## 7.4 Dosage Modification

There is no provision for dose modification of study intervention. If a participant interrupts intervention due to an AE, study intervention can be restarted in consultation with the Medical Monitor or designee.

# 7.5 Preparation/Handling/Storage/Accountability

The IP must be stored in a secure area according to local regulations. It is the responsibility of the investigator, or designee where permitted, to ensure that IP is only dispensed to study participants.

Clinical Protocol BMS-986165 IM011237 Deucravacitinib

The IP must be dispensed only from official study sites by authorized personnel according to local regulations.

The product storage manager should ensure that the study intervention is stored in accordance with the environmental conditions (temperature, light, and humidity) as determined by BMS. If concerns regarding the quality or appearance of the study intervention arise, the study intervention should not be dispensed, and BMS should be contacted immediately.

Study intervention not supplied by BMS will be stored in accordance with the package insert.

IP documentation (whether supplied by BMS or not) must be maintained that includes all processes required to ensure the drug is accurately administered. This includes documentation of drug storage, administration and, as applicable, storage temperatures, reconstitution, and use of required processes (eg, required diluents, administration sets).

- The investigator or designee must confirm appropriate temperature conditions have been maintained during transit for all study intervention received and any discrepancies are reported and resolved before use of the study intervention.
- The investigator, institution, or the head of the medical institution (where applicable) is responsible for study intervention accountability, reconciliation, and record maintenance (ie, receipt, reconciliation, and final disposition records).
- Further guidance and information for the final disposition of unused study interventions are provided in the Study Reference Manual.

#### 7.6 Treatment Compliance

When participants self-administer study intervention(s) at home, compliance with study intervention will be assessed at each visit. Compliance will be assessed by direct questioning, counting returned tablets, etc, during the site visits and documented in the source documents and relevant form. Deviation(s) from the prescribed dosage regimen should be recorded in the Case Report Form (CRF).

A record of the quantity of deucravacitinib/placebo dispensed to and administered by each participant must be maintained and reconciled with study intervention and compliance records. Intervention start and stop dates, including dates for intervention delays and/or dose reductions, will also be recorded in the CRF.

# 7.7 Concomitant Therapy

[figure not shown]
#### 7.7.1 Prohibited and/or Restricted Treatments

Prohibited and/or restricted medications taken during the study are described below.

- Exposure to any investigational drug, investigational vaccine, or placebo outside of the current study. Specifically, participants currently in other interventional studies for COVID-19, including investigational COVID-19 vaccination studies that are not authorized or approved by relevant Health Authorities, should not participate in BMS clinical studies
- Use of any medications/therapy that would aggravate psoriasis. These include agents such as lithium, antimalarials (quinacrine, chloroquine, and hydroxychloroquine), propranolol,

indomethacin, and quinidine unless it is considered necessary for the participant's welfare and/or intervention of an AE/SAE

- Use of opioid analgesics unless it is considered necessary for the participant's welfare and/or treatment of an AE/SAE
- Phototherapy; use of tanning booths or therapeutic sunbathing
- Any use of biologic medications (eg, adalimumab, etanercept, infliximab, ustekinumab).
- Any use of oral psoriasis medications (eg, apremilast, methotrexate, cyclosporine, retinoids, fumaric acid derivatives) for any indication
- Any use of oral or injectable corticosteroids (prednisone, methylprednisolone, etc), unless it is
  considered necessary for the participant's welfare and/or intervention of an AE/SAE
  Note: optic, ophthalmic, nasal, and inhaled corticosteroids within recommended doses and
  with no systemic effects are permitted.
- Any topical medications/interventions, which are used for any indication, that could affect psoriasis evaluation (including, but not limited to, high potency corticosteroids [WHO Classes I to V], > 3% salicylic acid, urea, alpha- or beta-hydroxy acids, anthralin, calcipotriene, vitamin D derivatives, retinoids, tazarotene, methoxsalen, trimethylpsoralens, pimecrolimus, and tacrolimus) and intralesional corticosteroids.

- Any medicated shampoos that contain corticosteroids, coal tar, > 3% salicylic acid, or vitamin D3 analogues
- Live attenuated vaccines (including, but not limited to, any live attenuated COVID-19 vaccines) should not be used during the study, including the safety follow-up period of 60 days following last dose of IP (see Section 7.7.4 for permitted vaccines).

#### 7.7.2 Permitted Concomitant Medications

Participants may take any medication that is not restricted by the protocol, is not expected to interfere with the conduct of the study and will not affect study assessments. Stable doses of concomitant medication for chronic medical conditions are permitted if neither the medication nor the medical condition meet exclusion criteria as detailed in Section 6.2. Dose adjustments of these

medications should be avoided during the study unless clinically indicated. If a dose adjustment of these medications should occur, they must be recorded on the Concomitant Medications eCRF. The investigator should instruct the participant to notify the study site about any new treatment he/she takes after the start of the study intervention. All medications and significant nondrug therapies (including physical therapy and blood transfusions) administered after the participant starts study intervention must be listed on the Concomitant Medications eCRF.

Concomitant medications (prescription, over the counter, or herbal) should be administered during the study only if they are to be used for treatment of specific medical reasons.

# 7.7.4 Permitted Vaccines (Including COVID-19 Vaccine)

Administration of a non-live vaccine is allowed during the study. However, the efficacy and safety of non-live vaccines (including non-live COVID-19 vaccines) in participants receiving deucravacitinib is unknown. The following are examples of non-live vaccines: inactivated vaccines (eg, heat-killed and formalin-killed vaccines), subunit vaccines (eg, influenza and pneumococcal vaccines), toxoid vaccines, nucleic acid vaccines that do not encode potentially infectious virus (eg, Pfizer/BioNTech and Moderna COVID-19 vaccines) and replication-incompetent recombinant vector vaccines (eg, AstraZeneca/University of Oxford COVID-19 vaccine).

For COVID-19 vaccines requiring more than 1 dose, the full series (eg, both doses of a 2-dose series) should be completed 30 days prior to enrollment. Ideally, AEs attributable to a vaccine should have resolved prior to enrollment.

If a participant receives a COVID-19 vaccination during the study, details such as type and date of vaccine received should be recorded on the concomitant medication page. For COVID-19 vaccines administered prior to enrollment, the types, details, and dates should be also recorded on the appropriate eCRF page.

Please contact the Medical Monitor or designee with any questions related to COVID-19 vaccines.

#### 7.8 Continued Access to Study Intervention After the End of the Study

At the end of the study, BMS will not continue to provide BMS-supplied study intervention to participants/investigators unless BMS chooses to extend the study. The investigator should ensure that participant receives appropriate standard of care to treat the condition under study.

#### 8 DISCONTINUATION CRITERIA

## 8.1 Discontinuation From Study Intervention

Participants MUST discontinue IP/IMP for any of the following reasons:

- Participant's request to stop study intervention. Participants who request to discontinue study intervention will remain in the study and must continue to be followed for protocol-specified follow-up procedures. The only exception to this is when a participant specifically withdraws consent for any further contact with him/her or persons previously authorized by the participant to provide this information
- Any clinical AE, laboratory abnormality, or intercurrent illness which, in the opinion of the investigator, indicates that continued participation in the study is not in the best interest of the participant
- Termination of the study by BMS
- Loss of ability to freely provide consent through imprisonment or involuntarily incarceration for treatment of either a psychiatric or physical (eg, infectious disease) illness.
  - Note: Under specific circumstances and only in countries where local regulations permit, a participant who has been imprisoned may be permitted to continue as a participant. Strict conditions apply, and BMS approval is required
- Abnormal liver tests suggestive of drug-induced liver injury (DILI), as defined in Section 9.2.8 or if the investigator believes that it is in the best interest of the participant
- The participant develops a malignancy, with the exception of a participant who develops non-melanoma skin cancer who may continue in the study at the discretion of the investigator
- Pregnancy, positive pregnancy test or participant expresses an interest in becoming pregnant (Section 9.2.6)
- Unblinding of a participant's intervention assignment for any reason (emergency or nonemergency)
- Inability or failure to comply with protocol requirements in the opinion of the investigator
- Participant reports suicidal ideation, suicidal behavior, or suicide attempts at any time after inclusion. The participant should then be immediately referred to a mental health professional for evaluation of suicide risk

Refer to the Schedule of Activities (Section 2) for data to be collected at the time of intervention discontinuation and follow-up and for any further evaluations that can be completed.

In the case of pregnancy, the investigator must immediately, within 24 hours of awareness of the pregnancy, notify the BMS Medical Monitor/designee of this event. The study treatment will be permanently discontinued. See Section 8.

All participants who discontinue study intervention should comply with protocol-specified follow-up procedures as outlined in Section 2. The only exception to this requirement is when a participant withdraws consent for all study procedures, including post-treatment study follow-up, or loses the ability to consent freely (eg, is imprisoned or involuntarily incarcerated for the intervention of either a psychiatric or physical illness).

If study intervention is discontinued prior to the participant's completion of the study, the reason for the discontinuation must be documented in the participant's medical records per local regulatory requirements in each region/country and entered on the appropriate CRF page.

#### 8.1.1 Temporary Discontinuation from Study Intervention

Temporary study intervention discontinuation is only allowed if the participant develops an AE which, in the opinion of the investigator, indicates that it is in the participant's best interest that the study intervention be placed on hold. Study intervention in this situation should be stopped until the AE is medically treated and has resolved per investigator's judgement.

Temporary interruption of study treatment should be implemented in the context of clinical suspicion for SARS-CoV-2 or a positive diagnostic test for SARS-CoV-2. When study treatment is interrupted in a confirmed case of SARS-CoV-2, the investigator, in consultation with the Medical Monitor, should determine whether the resolution of symptoms alone (ie, without repeat diagnostic testing for SARS-CoV-2) is sufficient to resume study treatment.

Temporary interruption of study intervention may be considered in the event of SARS-CoV-2 vaccination according to local guidelines. To facilitate reporting of SARS-CoV-2 events that occur during the study, all AEs and SAEs related to SARS-CoV-2 must be reported from the time of consent. In addition, AEs or SAEs will trigger additional data collection through dedicated eCRF pages, which will allow the Sponsor to further evaluate these events.

Any temporary study intervention discontinuation as well as restart must be documented on the corresponding eCRF.

## 8.1.2 Post-Study Intervention Study Follow-up

In this study, efficacy is a key endpoint of the study. Post-study follow-up is of critical importance and is essential to preserving participant safety and the integrity of the study. Participants who discontinue study intervention must continue to be followed in this study for collection of outcome data as required and in line with Section 5 until the conclusion of the study.

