## **Overall Design:**

This is a Phase 4, multicenter, randomized, double-blind placebo-controlled study comparing the effect of deucravacitinib versus placebo on QoL in patients with moderate-to-severe plaque psoriasis and impaired HRQoL. Participants will undergo screening evaluations within 28 days prior to administration of study intervention to determine eligibility. Following the screening process, approximately 174 participants will be randomized in a 2:1 ratio to either deucravacitinib 6 mg once daily (QD) or placebo, respectively.

It is estimated that approximately 90% of randomized participants (ie, approximately 156 participants) would have baseline s-PGA scores  $\geq$  3.

The duration of study participation is approximately 60 weeks and will be divided into the following periods: screening (up to 4 weeks), treatment (52 weeks), and follow-up (4 weeks).

At Week 16, all participants regardless of their blinded intervention, will be switched to open-label deucravacitinib 6 mg QD bottles through Week 52. Participants and investigators remain blinded to double-blind placebo-controlled period study intervention until the end of the study at Week 52.

Participants will be followed up for safety for 4 additional weeks, from Week 52 through Week 56. Participants who discontinue study intervention early/withdraw prematurely must complete the end of treatment visit. The participant will be asked to return to the clinic to complete the 28-day safety follow-up visit and encouraged to report any serious adverse events or adverse events experienced during this time.

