		Serum (minimum sensitivity equivalent units 25 IU/L or equivalent units of hCG) to be done at the Screening Visit.
		The participant must be excluded from participation if the serum pregnancy result is positive.
		If needed to document postmenopausal status, as defined in Section 9.4.
FSH	X	Females under the age of 55 years must have a serum FSH level > 40 mIU/mL to confirm menopause.
AE Reporting	-	
Monitor for SAEs	X	All SAEs must be collected from the date of participant's written consent until 30 days post discontinuation of dosing or participant's participation in the study if the last scheduled visit occurs at a later time. All AE (SAEs or nonserious AE) related to SARS-CoV-2 infection collected from time of consent.
AE, adverse event;		BMI, body mass index;
ECG, electrocardiogram;	teractive response technolo	FSH, follicle-stimulating hormone; hCG, human chorionic gonadotropin;
PE, physical examination;		
SAE, serious adverse eve		acute respiratory syndrome coronavirus 2; Organization; WOCBP, women of childbearing potential.

Table 2-2: Day -14 and On-Intervention Procedural Outline (IM011237), Day 1 Through Week 20

Procedure	Week -2 D -14 (±1 d) Visit 1	Day 1 Visit 2	Week 1  D8  (±3 d)  Visit 3	Week 2 D15 (±3 d) Visit 4	Week 4 D29 (±3 d) Visit 5	Week 8 D57 (±3 d) Visit 6	Week 12 D85 (±3 d) Visit 7	Week 16 D113 (±3 d) Visit 8	Week 20 D141 (±3 d) Visit 9	Notes
Eligibility Assessments										
Inclusion/Exclusion Criteria		X								
Medical History		X								
Safety Assessments	•									
Targeted PE		X	X	X	X	X	X	X	X	
Body Weight		X						X		
Vital Signs	X	X	X	X	X	X	X	X	X	
Concomitant Medication Use	X	X	X	X	X	X	X	X	X	
AE Reporting										
Monitor for SAEs	X	X	X	X	X	X	X	X	X	
Monitor for Nonserious AEs		X	X	X	X	X	X	X	X	

Table 2-2: Day -14 and On-Intervention Procedural Outline (IM011237), Day 1 Through Week 20

Procedure	Week -2 D -14 (±1 d)	Day 1 Visit 2	Week 1 D8 (±3 d)	Week 2 D15 (±3 d)	Week 4 D29 (±3 d)	Week 8 D57 (±3 d)	Week 12 D85 (±3 d)	Week 16 D113 (±3 d) Visit 8	Week 20 D141 (±3 d) Visit 9	Notes
Laboratory Tests	Visit 1		Visit 3	Visit 4	Visit 5	Visit 6	Visit 7	V ISIT O	VISIT	
Laboratory Tests										
Pregnancy Test (Urine)		X			X	X	X	X	X	WOCBP only
Efficacy Assessments	1	1					1			
PASI		X	X	X	X	X	X	X	X	
s-PGA		X	X	X	X	X	X	X	X	
ss-PGA		X	X	X	X	X	X	X	X	
PGA-F		X	X	X	X	X	X	X	X	
pp-PGA		X	X	X	X	X	X	X	X	
I-s-PGA		X	X	X	X	X	X	X	X	
s-PGA-G		X	X	X	X	X	X	X	X	
sf-PGA		X	X	X	X	X	X	X	X	

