#### 5.1.2 Intervention Period

Participants who have completed the screening procedures and have met the inclusion/exclusion criteria will be randomized on Day 1 in a 2:1 ratio to either deucravacitinib 6 mg QD or placebo, respectively.

Dummy tablets (placebo to deucravacitinib 6 mg tablets) will be administered to participants to maintain blinding (Section 7.1).

All participants will receive a wristwatch to monitor sleep quality for 14 days prior to Day 1 to be worn for 14 days. This wristwatch will be returned to the study site on Day 1 as listed in the Schedule of Activities (Section 2). This wristwatch will be returned to all participants again on Weeks 12 and 40 to be worn for 14 days prior to Week 16 and Week 52 and will be returned to the study sites as per the Schedule of Activities (Section 2).

#### 5.1.3 Week 16

All efficacy endpoints and safety will be assessed at Week 16. At Week 16, all participants, regardless of their blinded intervention, will be switched to open-label deucravacitinib 6 mg QD bottles through Week 52. All participants will return their wristwatches at the Week 16 visit.

#### 5.1.4 Week 20

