#### 5.1.5 Week 52 and Safety Follow-up Period

[figure not shown]
The safety follow-up period is a 28-day window after the Week 52 visit. The participant will be encouraged to report any SAEs or AEs experienced during this time.

The end of treatment (EOT) visit will be completed for participants who discontinue study intervention early. The participant will be asked to return to the clinic to complete the 28-day safety follow-up visit.

All participants will return their wristwatches at the Week 52 visit.

The study design schematic is presented in Figure 5.1.5-1.

Figure 5.1.5-1: Study Design Schema

PBO, placebo; QD, once daily.

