## 8.2 Discontinuation From the Study

Participants who request to discontinue study intervention will remain in the study and must continue to be followed for protocol-specified follow-up procedures. The only exception to this is when a participant specifically withdraws consent for any further contact with him/her or persons previously authorized by participant to provide this information.

- Participants should notify the investigator of the decision to withdraw consent from future follow-up.
- The withdrawal of consent should be explained in detail in the medical records by the investigator, as to whether the withdrawal is from further treatment with study intervention only or also from study procedures and/or post-treatment study follow-up, and entered on the appropriate CRF page.
- In the event that vital status (whether the participant is alive or dead) is being measured, publicly available information should be used to determine vital status only as appropriately directed in accordance with local law.
- If the participant withdraws consent for disclosure of future information, the Sponsor may retain and continue to use any data collected before such a withdrawal of consent.

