#### 8.2.1 Individual Discontinuation Criteria

- A participant may withdraw completely from the study at any time at his/her own request, or may be withdrawn at any time at the discretion of the investigator for safety, behavioral, compliance, or administrative reasons. This is expected to be uncommon. Stopping study intervention is not considered withdrawal from the study.
- At the time of discontinuing from the study, if possible, an early termination visit should be conducted, as shown in the Schedule of Activities (Section 2). See the Schedule of Activities (Section 2) for data to be collected at the time of study discontinuation and follow-up and for any further evaluations that need to be completed.
- The participant will be permanently discontinued both from the study intervention and from the study at that time.
- If the participant withdraws consent for disclosure of future information, the Sponsor may retain and continue to use any data collected before such a withdrawal of consent.

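### Minor: safety summaries after stopping treatment end at day 28 although SAEs are collected for at least 30 days, and Week 16 attendance and off-treatment itch scores need one stated rule

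*Combined protocol and SAP*

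**What the plan says.** **Safety cut-off.** The safety row of Table 10.3-1 includes post-discontinuation data only up to day 28 after the last dose. Section 9.2.2 requires SAEs to be collected for 30 days after dosing stops. Table 2-1 says the same and extends collection if the last scheduled visit is later. Footnote a of Table 2-3 places the safety visit 28 days after the last dose, plus or minus 3 days.

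**Week 16 after stopping intervention.** Section 8.1.2 says that participants who stop "must continue to be followed in this study for collection of outcome data as required and in line with Section 5 until the conclusion" (to study end). Section 8.2 says: "Participants who request to discontinue study intervention will remain in the study and must continue to be followed for protocol-specified follow-up procedures". Section 8.2.1 adds: "Stopping study intervention is not considered withdrawal from the study". Section 5.1.3 states: "All efficacy endpoints and safety will be assessed at Week 16", and exempts no one. Section 8.1, however, points to the schedule: "All participants who discontinue study intervention should comply with protocol-specified follow-up procedures as outlined in Section 2". The rule for early stoppers visible there is footnote a of Table 2-3, with an EOT/ET visit and the safety visit. The Overall Design text in Section 1 ("Participants who discontinue study intervention early/withdraw prematurely must complete the end of treatment visit") and Section 5.1.5 ("The participant will be asked to return to the clinic to complete the 28-day safety follow-up visit") name the same two visits. The Week 16 analysis trigger in Section 1 (Statistical Methods), Section 7.3.1 and Section 10.6 accepts discontinuation before Week 16 in place of a completed Week 16 visit.

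**Itch NRS.** Section 1, Table 10.4.1-1 and Table 10.4.3-1 apply multiple imputation to missing data. Table 10.3-1 applies it to participants who discontinue before Week 16, although the same row opens by taking in all data available up to the database lock. Table 10.4.1-1 gives the strategy for discontinuation as a composite variable.

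**The concern.** The plan keeps people who stop treatment in the study, then describes their visits, imputation and safety window in places that do not fully agree.

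- The safety cut-off is a stated rule. Applied literally, an SAE on day 29 or 30 after the last dose must be collected but does not enter the summary tables.
- A site that follows only the named visits may not see an early stopper at Week 16. An itch score not taken then cannot be recovered later.
- If an off-treatment itch score is taken, the tables should say plainly whether it is analysed. Itch NRS is a key secondary endpoint, formally tested in both the Overall Population and the s-PGA ≥ 3 Sub-Population.

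**Working it through.** The plan states no figure of its own to reproduce here. The check is day arithmetic on the schedule and a comparison of the passages.

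**1. Safety window (days after last dose)**
- Summary cut-off: day 28 (Table 10.3-1).
- SAE collection: at least day 30 (Section 9.2.2, Table 2-1).
- Safety visit: 28 − 3 = day 25 to 28 + 3 = day 31 (Table 2-3, footnote a).
- Days on which SAEs are collected but not summarised: at least 30 − 28 = 2 (days 29 and 30), or 31 − 28 = 3 if the safety visit is on day 31. Table 2-1 can extend collection further for someone who stays in the study. Section 9.2.2 collects nonserious AEs to the final visit, so those can also fall outside the cut-off.

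**2. Named visits against Week 16**

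Table 2-2 gives "Week 16 D113 (±3 d) Visit 8", so the window is 113 − 3 = D110 to 113 + 3 = D116. For a last dose on day L, the safety visit falls between L + 25 and L + 31.
- Entirely before the window: L + 31 ≤ 109, so L ≤ 78.
- Can fall inside it: L + 31 ≥ 110 and L + 25 ≤ 116, so 79 ≤ L ≤ 91.
- Entirely after it: L + 25 ≥ 117, so L ≥ 92.

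| Last dose | Safety visit | Relative to D110–D116 |
|---|---|---|
| D57 (Week 8) | D82–D88 | before |
| D78 | D103–D109 | before |
| D85 (Week 12) | D110–D116 | inside |
| D92 | D117–D123 | after |

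The EOT/ET visit has no stated day. I take it to come no later than the safety visit. On that basis, for any last dose by D78 both named visits precede Week 16. For D79 to D91 the safety visit may fall in the window, but Table 2-3 marks s-PGA at EOT/ET and not at the safety visit; the DLQI and itch rows are not visible. For someone who stops close to Week 16, the EOT/ET visit may itself fall in the window.

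**3. Which endpoints depend on this**

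Table 10.4.1-1 counts discontinuation of intervention or study before Week 16 as non-response for DLQI 0/1, the 4-point DLQI reduction and s-PGA 0/1. Attending or missing Week 16 changes none of these. Only itch NRS, and any sensitivity analysis that uses off-treatment data, can change.

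**4. Participant count, by assumption only**

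No discontinuation rate is visible. Assume that 5% to 15% stop before Week 16 and that 50% to 70% of those stay in the study.
- Overall (174): 174 × 0.05 = 8.7 and 174 × 0.15 = 26.1 stop; 8.7 × 0.5 = 4.4 and 26.1 × 0.7 = 18.3 stay, so about 4 to 18.
- s-PGA ≥ 3 (about 156): 156 × 0.05 = 7.8 and 156 × 0.15 = 23.4 stop; 7.8 × 0.5 = 3.9 and 23.4 × 0.7 = 16.4 stay, so about 4 to 16.

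These are upper counts under the assumptions, because some who stop late would have an EOT/ET visit in the window.

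**5. Itch wording**

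Imputing only missing values and keeping observed off-treatment scores is a treatment-policy handling of discontinuation. Setting observed scores aside and imputing them is closer to a hypothetical strategy, depending on the imputation model. A composite strategy makes discontinuation itself part of the outcome, and multiple imputation of missing data does not do that. The described method and its label therefore point to different estimands.

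**The case against.** Much of the other side stands.

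- **Week 16.** Section 8.1.2, read with Sections 5.1.3, 8.2 and 8.2.1, already implies attendance. The EOT/ET and safety visits are additions, and nothing cancels a scheduled visit. Many schedule notes are redacted and may settle the matter. A reader might infer that the protocol contradicts itself, or that early stoppers are released from Week 16; the documents support neither. What remains is that the visible visit text and the analysis trigger lean the other way from Section 8.1.2.
- **Itch.** A reader might infer from Table 10.3-1 that observed off-treatment scores are discarded. That reading is strained, because the row starts from all available data and three other places speak of missing data. Section 10.4 also leaves missing-data procedures to the SAP, whose text is not in the file reviewed. The mismatch with the composite label remains.
- **Safety.** Day 28 matches the nominal safety visit, so it does not conflict with the protocol at large. A summary window may be deliberately shorter than the collection window, and individual SAE reporting is untouched. But no reason is stated, and the cut-off falls short of both the 30-day duty and the latest permitted visit. The general statement in Section 10.4.5 that safety is analysed to the end of study does not lift this specific limit.

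**Conclusion.** The point holds as a minor one, in three parts of unequal weight.

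1. The safety cut-off is the firmest: at least days 29 and 30 after the last dose lie inside required SAE collection and outside the summaries. A reader might turn this into a lost fraction of the collection period. The documents do not support one, since Table 2-1 lets collection run past day 30. They also give no event rate.
2. Week 16 attendance is a matter of reconciliation. It rests on the visible text and on the EOT/ET visit coming no later than the safety visit.
3. For itch, the text points to imputing only missing values, but the strategy label does not fit that.

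A reader might infer a threat to the primary endpoint. There is none, because early stoppers are non-responders whether or not they attend. The effect on the itch comparison cannot be sized: no discontinuation rate, itch standard deviation or expected itch difference is visible. The counts of 4 to 18 and 4 to 16 are assumptions about how many people are concerned and say nothing about bias or power.

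**What to change.** 1. In the safety row of Table 10.3-1, replace day 28 with a fixed window covering the required SAE collection: at least 30 days after the last dose, or through the safety follow-up visit if later. A fixed window avoids drawing long off-treatment follow-up into the summaries. If day 28 is deliberate, say so and list later SAEs separately.
2. Check the unredacted schedule notes. If they do not settle the matter, reconcile Sections 1, 2, 5.1.5 and 8.1.2 with a schedule footnote: participants who stop intervention before Week 16 but stay in the study complete the Week 16 assessments on the original date, at minimum the itch NRS.
3. Make the itch row of Table 10.3-1 and the strategy in Table 10.4.1-1 agree on whether observed off-treatment Week 16 scores are used. If they are, label discontinuation as treatment policy and impute only missing values. If they are not, say that they are set aside and use a label that fits.

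The cost is one changed cut-off, one footnote, and one reworded row with its label. Any added visit concerns few participants and is one that Section 8.1.2 already implies.
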